6. STUDY SUBJECTS

6.1. Disposition of Subjects

Subject disposition will be summarized for study 8HA01EXT for subjects from each parent study and overall. This table will present the number of subjects in the All-enrolled Analysis Set, the number and percentage of subjects enrolled in the Full Analysis Set (FAS) including the number of subjects with an efficacy period, the number of subjects within each treatment regimen, the number and percentage of subjects in the Safety Analysis Set, and the number and percentage of subjects in the surgery subgroup. The number of subjects with the status of completed, and discontinued from the study, including the primary reason for those who discontinued, will be tabulated. Subject disposition, including the date of the last visit and the reason for early termination for subjects who did not complete the study, will be provided in a data listing.

The number and percentage of enrolled subjects will be summarized by country, site and treatment regimen using All-enrolled Analysis Set. The number of subjects attending each visit in study 8HA01EXT will be summarized overall by planned visit using the Safety Analysis Set. The summary for each study visit will include only those subjects for whom the visit evaluations reflect the designated visit on the study (i.e., including subjects for whom this visit represents the end-of-study visit due to early termination).

6.2. Demography and Baseline Disease Characteristics

Demographics and baseline disease characteristics will be summarized using the Safety Analysis Set.

6.2.1. Demography

Demographic characteristics including age (years), geographic location, height (cm), weight (kg), and body mass index (kg/m^2) will be summarized using the data at entry into study 8HA01EXT. Race and ethnicity will also be included in the summary using the data at the entry into the parent study. Geographic locations are defined as Europe, North America, and other. For subjects from studies 997HA301/997HA307, Europe includes Austria, Belgium, Germany, France, United Kingdom, Italy, Spain, Sweden and Switzerland. North America includes Canada and the United States. Other countries include Australia, Brazil, Hong Kong, India, Japan, Israel, New Zealand and South Africa. For subjects from study 8HA02PED, Europe includes Ireland, the Netherlands, Poland, and the United Kingdom. North America includes the United States. Other countries include Australia, Hong Kong, and South Africa. For subjects from study 997HA309, there are only two countries: Australia and New Zealand, which will be categorized as 'Other'.

6.2.2. General Medical and Surgical History

An updated medical and surgical history is collected at the first visit of study 8HA01EXT. A summary of this updated medical and surgical history by body system for the Safety Analysis Set

will be presented. A subject will be counted only once if they reported one or more occurrences in the same body system.

6.2.3. Physical Examination

Physical examination continues to be performed annually in this extension study. A listing of subjects with an abnormal status will be presented.

6.3. Protocol Deviations

All protocol deviations will be recorded throughout study 8HA01EXT. Major and minor protocol deviations/violations are to be pre-specified prior to database lock. All major protocol deviations during study 8HA01EXT will be summarized by study 8HA01EXT treatment regimen, the surgery subgroup, and overall using the FAS. Protocol deviations that occurred during surgical/rehabilitation periods will be attributed to the surgery subgroup only. All deviations, both major and minor, will be provided in a data listing.

In addition, another set of protocol deviations (PDs) will be determined using the EPD dataset created for the impact analysis, where changes requiring subject confirmation have been reverted to the original pre-change state. Details specific to the impact analysis will be provided in Sections 9 below. This set of PDs will be summarized and listed in a similar manner to the primary set, for the FAS.

6.4. Non-study Drug Medications

6.4.1. Concomitant Medications

Two listings will be provided, one for concomitant medications taken through the Final Study Visit/Early Termination Visit and the other for concomitant medications taken after the Final Study Visit/Early Termination Visit and prior to the Follow-up visit/phone call.

Concomitant medications will be summarized using for the Safety Analysis Set.

Concomitant medications are those administered on or after 8HA01EXT Study Day 1, or administered prior to 8HA01EXT Study Day 1 and ongoing at the start of 8HA01EXT Study Day 1. They will be characterized based on the start and end dates relative to 8HA01EXT Study Day 1. Medications reported for a subject will be classified as concomitant unless they can be excluded as such, as follows:

- Medications with a start date after the follow-up visit will not be considered concomitant.
- For partial dates, if a concomitant medication start day is missing then the medication will be assumed to be a concomitant medication unless the start month and/or year or medication stop date can be used to determine if a medication is concomitant, as follows.
 - If the concomitant medication start day is missing, but the month and year are before the start month and year of 8HA01EXT Study Day 1 and the concomitant medication stop date is before the date of 8HA01EXT Study Day 1, then the medication will not be classified as concomitant.

- If the day of the start date is missing and the month and year are after the month and year of 8HA01EXT Study Day 1, then the medication will be classed as concomitant.
- If the month of the start date is missing and the year is before the start year of 8HA01EXT Study Day 1 and the stop date is before the date of 8HA01EXT Study Day 1, then the medication will not be classified as concomitant.

Concomitant medications will be coded using World Health Organization drug enhanced dictionary version March 2011.

6.4.2. Other Therapies and Procedures

Other therapies administered and concomitant procedures performed in study 8HA01EXT will be summarized using for the Safety Analysis Set as well as will be listed.

6.5. Study Drug

Study treatment regimens are described in Section 3.2. The listing of all study drug administered will include the reason for administration (prophylaxis [regular or additional], treatment of a bleeding episode, surgery, other). Subject-level information on dosing with study drug will also be provided in a data listing.

Treatment with study drug, (exposure, prophylactic dose, prophylactic dosing interval, and consumption) will be summarized using the FAS.

6.5.1. Exposure

6.5.1.1. Duration of rFVIII Fc Dosing, Number of Injections and Exposure Days to rFVIII Fc

Two summaries of exposure will be produced. Details of the summaries are described in Section 7.3.2.

6.5.1.2. Last Prescribed Dose and Dosing Frequency

Subjects' last prescribed dose and dosing frequency will be summarized as a cross tabulation of dosing frequency by dose (IU/kg) in which the number and percentage of subjects who were last prescribed each combination of dose and dosing frequency (every 2, 3, 4, or 5 days or twice weekly) will be tabulated. A summary table will be provided for the overall prophylaxis regimen consisting of the tailored prophylaxis and weekly prophylaxis regimens in study 8HA01EXT. The last prescribed dose will also be summarized for each dosing frequency using descriptive statistics. If no dose (dosing frequency) changes were prescribed, then a subject's starting dose (dosing frequency) will be used. The dose for the twice weekly regimen will be the average of the two doses given. Percentages will be based on the number of subjects in each prophylactic regimen (ie, not on the number of subjects in each dosing frequency category).

6.5.2. Change of Treatment Regimens

For the changes in treatment regimens in study 8HA01EXT described in Section 5.3.1, the number of subjects with at least one treatment regimen change, the regimen first changed to, and the number of changes will be summarized by starting treatment regimen in study 8HA01EXT and overall.

6.5.3. Prophylactic Dose (IU/kg) and Dosing Interval (days)

Because prophylactic dosing in study 8HA01EXT is based on variable doses and dosing intervals, the amount of rFVIII^{FC} received prophylactically will be summarized as an average weekly dose. Descriptive statistics will be provided using the FAS for each prophylactic regimen.

The average weekly prophylactic dose (IU/kg) and the prophylactic dosing interval will be based on prophylactic doses that are not separated by a bleeding episode. Data to be included in the calculations, specifically the prophylactic doses and the total duration of prophylaxis treatment, will come strictly from intervals representing 2 consecutive prophylactic doses (PR) during the efficacy period (see Section 5.3.2 for a description of the efficacy period). The sum of doses at PR_x and the sum of interval durations (PR_{x+1} minus PR_x) will be determined across all evaluable intervals of PR_x to PR_{x+1}. As such, when a bleeding episode is encountered, the interval stops at the prophylactic dose prior to the event and continues with the first prophylactic dose after the event. The last PR dose during a given treatment regimen will be the end of the last interval used for these calculations. The start and stop time of a treatment regimen and the calculation of total duration in that treatment regimen are described in Section 5.3.1. If a subject is treated in a given treatment regimen more than once during study 8HA01EXT, the sum of doses at PR_x, sum of days in PR intervals, sum of days in PR intervals and number of PR intervals will be calculated across all durations in that treatment regimen before the average weekly prophylactic dose and dosing interval are calculated using the formulae below.

$$\text{Average weekly prophylactic dose} = \frac{\text{Sum of doses at PR}_x}{\text{Sum of days in PR intervals}} \times 7$$

$$\text{Average prophylactic dosing interval} = \frac{\text{Sum of days in PR intervals}}{\text{Number of PR intervals}}$$

For the personalized prophylaxis regimen, additional injections administered will also be included in the average weekly prophylactic dose and average dosing interval calculations.

Prophylactic dosing will be further characterized by the number of prescribed changes in the dose and the number of prescribed changes in the dosing interval while on a given prophylaxis treatment regimen. If both dose and dosing interval change, they will be included in each summary. Dose and dosing interval changes are based on recommendations made by the Investigator and may or may not reflect whatever modifications a subject actually made to his dosing regimen. The number of prescribed changes in the dose level and the number of prescribed changes in the dosing schedule will be summarized categorically (0, 1, 2, 3, 4, >4) and with descriptive statistics. If a subject is treated in a given treatment regimen more than once during study 8HA01EXT, then the total number of changes will be across all durations in that treatment regimen.

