5.3.2.3. Option 3: Personalized Prophylaxis

If optimal prophylaxis dosing cannot be achieved using either of the above options, the Investigator may further personalize dosing to meet the needs of individual subjects.

The Investigator may consider the following personalized dosing options:

- Addition of "prevention" doses prior to strenuous activity.
- Targeting a FVIII trough level of >3%, if the bleeding history and/or activity level requires.
- Dosing less frequently.

The Investigator is not limited to the options above, and should consult the Medical Monitor for further consideration of a subject's dosing options. The personalized prophylaxis dosing option will require consultation with the Medical Monitor.

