3.2.1.2. Prophylaxis Regimens

Details for each dosing option, including, if applicable, date of change, new dose and/or dosing interval, and reason(s) for the regimen change will be recorded on the appropriate eCRF each time a change is made.

Option 1: Tailored Prophylaxis

The Investigator may consider the following options for tailored prophylaxis to target a FVIII trough of up to 5%, but is encouraged to use the lowest effective dose targeting a FVIII trough level between 1% and 3%. If bleeding episodes occur at FVIII trough levels of 1% to 3%, further adjustments to dose or interval over the course of the study will target trough levels of up to 5%.

Dosing options are:

- approximately 25 IU/kg to 65 IU/kg every 3 to 5 days
- or dosing 2 times per week at approximately 20 IU/kg to 65 IU/kg on Day 1 and 40 IU/kg to 65 IU/kg on Day 4

The dose and interval should be based on the subject's clinical profile observed in the preceding rFVIIIFc study, and/or his individual PK (if available), and FVIII trough and/or peak (recovery) values.

In pediatric subjects, doses may be adjusted up to a maximum prophylactic dose of 80 IU/kg and the interval decreased to every 2 days, if necessary to maintain adequate FVIII activity trough levels and prevent spontaneous bleeding events.

Option 2: Weekly Prophylaxis

Dosing is approximately 65 IU/kg at weekly intervals. The dose should be based on the subject's clinical profile observed in the parent rFVIIIFc study, and/or his individual PK (if available), and FVIII trough and/or peak (recovery) values. Subjects <12 years of age at entry to 8HA01EXT will not be offered this option initially but may be prescribed this weekly prophylaxis regimen once they reach the age of 12 years during the study.

Option 3: Personalized Prophylaxis

If optimal prophylaxis dosing cannot be achieved using either of the above options, the Investigator may further personalize dosing to meet the needs of individual subjects.

The Investigator may consider the following personalized dosing options:

- Addition of "prevention" doses prior to strenuous activity

- Targeting a FVIII trough level of >3%, if the bleeding history and/or activity level requires
- Dosing less frequently

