- For subjects on the episodic regimen following the end of a surgical/rehabilitation period, the efficacy period for the episodic regimen starts or re-starts (depending on whether there is a treatment regimen change during the surgical/rehabilitation period) at 00:01 on the day following the end of the surgical/ rehabilitation period.

Start and end dates/times for the efficacy period for given treatment regimens and treatment regimen changes will be adjusted for each surgery (major or minor) as necessary.

For subjects on a prophylactic regimen before the start of a surgical/rehabilitation period, the interval of time between the last dose before a surgical/rehabilitation period and the start of the surgical/rehabilitation period will not be attributed to the efficacy period for the prophylactic regimen. By definition, there should not be any treated bleeding episodes in this interval of time.

For subjects on a prophylactic regimen following the end of a surgical/rehabilitation period, bleeding episodes that occur after discharge from a rehabilitation facility but before the next prophylactic dose will be attributed to the surgical/rehabilitation period and hence not counted towards the annualized bleeding rate.

Adjustments Due to Large Injection Intervals

For analysis purposes, the efficacy period will also be adjusted to account for large intervals between injections resulting from missing data. Time between any 2 adjacent rFVIIIFc injections of greater than 28 days within a prophylactic treatment regimen will be removed from the efficacy period. The efficacy period prior to each such interval will end at the time of the first

injection of this interval and restart (or start if it is the first interval of a treatment regimen) at the time of the second injection of this interval. The efficacy period will be adjusted for each identified interval that is not within a surgical/rehabilitation period. Treatment regimens considered for large interval adjustment include tailored prophylaxis, weekly prophylaxis and personalized prophylaxis regimen with at least 2 routine prophylactic injections (additional injections are not considered due to the sporadic nature of these injections). No adjustment for large injection intervals will be made for episodic treatment regimens.

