6.5.5.2. Compliance of Prophylactic Injections

The compliance rate of each subject to the prescribed prophylactic dosing regimen during the efficacy period will be calculated in 2 ways, as dose compliance and as dosing interval compliance. Compliance will first be determined on a per-injection basis and then on a per-subject basis. That is, compliance for an individual dose or dosing interval will be determined and then the overall percentage of doses and dosing intervals that were in compliance will be determined for each subject.

For the purpose of evaluating compliance, the following will be considered per injection:

- the nominal dose taken compared to the nominal dose prescribed
- the actual day of treatment compared to the prescribed day of treatment

An individual dose will be considered compliant if it is within 80% to 125% of the prescribed dose. An individual dosing interval will be considered compliant if the time between two prophylactic doses is within 24 hours of the prescribed dosing interval. Prescribed dose and dosing intervals are according to the Investigator. Instructions provided to the subject by the Investigator regarding dose or dosing interval changes will be used to determine compliance as of the date the information was provided to the subject.

The actual dosing intervals will be calculated as the length of time between consecutive prophylactic doses (date/time of PR_{x+1} – date/time of PR_x). PR_{x+1} and PR_x are also discussed in Section 6.5.3. The actual time between doses will be determined in minutes and converted to days as the number of minutes divided by 1440. The prescribed dosing interval will be taken from the eCRF as recorded by the Investigator. The absolute value of the difference between the actual and prescribed dosing intervals must be ≤1 day (+/- 24 hours) in order to be compliant.

All prophylactic injections will be used to determine prophylactic dose compliance; only the prophylactic injections used to determine the average prophylactic dosing interval (i.e., intervals

not separated by a bleeding episode or surgical/rehabilitation period), as detailed in Section 6.5.3, will be used to evaluate prophylactic interval compliance. Dose and dosing interval compliance rates per subject will be determined as follows:

$$\text{Dose compliance rate} = \frac{\text{Number of doses taken within 80\% to 125\% of prescribed dose}}{\text{Total number of doses}} \times 100$$

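### Under personalized prophylaxis, permitted prevention doses create failing dosing intervals, so a subject who keeps every scheduled dose can be classed interval-non-compliant

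*SAP*

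**What the plan says.** - **Prevention doses are allowed.** Protocol 5.3.2.3 and SAP 3.2.1.2 list, among the options for personalized prophylaxis, extra "doses prior to strenuous activity". SAP 6.5 lists the recorded reasons for an injection as "prophylaxis [regular or additional], treatment of a bleeding episode, surgery, other", so regular and additional prophylaxis can be told apart in the data.
- **They enter the interval.** SAP 6.5.3 builds the average dosing interval from gaps between consecutive prophylactic doses with no bleed between them. For one regimen only it adds: "For the personalized prophylaxis regimen, additional injections administered will also be included in the average weekly prophylactic dose and average dosing interval calculations".
- **The same intervals feed compliance.** SAP 6.5.5.2 bases interval compliance on "only the prophylactic injections used to determine the average prophylactic dosing interval", which, "as detailed in Section 6.5.3, will be used to evaluate prophylactic interval compliance". A gap passes if it is "within 24 hours of the prescribed dosing interval", in either direction, and the prescribed interval is the one the Investigator recorded in the eCRF. A subject passes if his rate is at least 80%.
- **A second definition appears in the formula.** The numerator of the interval compliance rate in SAP 6.5.5.2 counts doses against the prescribed day and time, while its denominator counts intervals.
- **They are set aside elsewhere.** For the rule on gaps longer than 28 days, SAP 5.3.2 says "additional injections are not considered due to the sporadic nature of these injections".

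**The concern.** SAP 6.5.5 presents prophylactic compliance as adherence to what the Investigator recommended. A prevention dose falls between two scheduled doses. Once it is counted, one interval that was kept on time becomes two shorter ones, and each is tested against the full prescribed interval. The subject loses compliance for using an option that the regimen offers.

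Two descriptive outputs are at stake. The first is the interval compliance rate, with the three-way classification built on dose and interval compliance. The second is the average dosing interval for personalized prophylaxis, which follows a different rule from the tailored and weekly regimens. The table of last prescribed dosing frequency in SAP 6.5.1.2 covers only tailored and weekly prophylaxis, so the 6.5.3 average is the only planned summary of interval length for personalized subjects.

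**Working it through.** The documents give no figure on this point, so there is none to reproduce. I apply the SAP's rules to a subject who keeps every scheduled dose exactly on time and spends his whole efficacy period on personalized prophylaxis.

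**Inputs.** From SAP 6.5.5.2: tolerance of 1 day in either direction and a subject-level cut-off of 80%. Assumed, because the documents do not give them: prescribed interval P days, one prevention dose in every n scheduled intervals, taken x days after the preceding regular dose.

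**Step 1: which parts fail.** The split interval has parts x and P - x.
- The first part passes if P - x ≤ 1, that is, x ≥ P - 1.
- The second part passes if P - (P - x) = x ≤ 1.
- Both pass only if P - 1 ≤ x ≤ 1, which requires P ≤ 2.

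So for any P above 2 days at least one part fails. Both fail when 1 < x < P - 1. At P = 2, a prevention dose exactly at day 1 leaves both parts compliant.

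**Step 2: the subject's rate.** The n scheduled intervals become n + 1 observed intervals.
- Both parts fail: (n-1)/(n+1), below 0.80 when 0.2n < 1.8, so n ≤ 8.
- One part fails: n/(n+1), below 0.80 when 0.2n < 0.8, so n ≤ 3.
- Formula wording, counting regular doses as on schedule and the prevention dose as not: also n/(n+1).

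**Step 3: the average interval.** The total time is unchanged and there is one more interval, so the average is P × n/(n+1), whatever the value of x.

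| n | Rate, both parts fail | Rate, one part fails or formula wording | Average interval, P = 4 days |
|---|---|---|---|
| 3 | 50.0% | 75.0% | 3.00 |
| 4 | 60.0% | 80.0% | 3.20 |
| 5 | 66.7% | 83.3% | 3.33 |
| 8 | 77.8% | 88.9% | 3.56 |
| 9 | 80.0% | 90.0% | 3.60 |
| 12 | 84.6% | 92.3% | 3.69 |

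In calendar terms, n = 8 is one prevention dose every 24, 32 or 40 days for P = 3, 4 or 5, and n = 3 is one every 9, 12 or 15 days.

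**Step 4: between the two cases.** At P = 4 both parts fail only if 1 < x < 3, which is half of the interval if timing is uniform (an assumption). The expected rate is then (n-0.5)/(n+1), below 80% for n ≤ 6, or one prevention dose every 24 days.

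**Step 5: a frequent user.** One prevention dose a week means a share f = P/7 of intervals is split. The rate is (1-f)/(1+f) if both parts fail and 1/(1+f) otherwise: 40.0% and 70.0% at P = 3, and 16.7% and 58.3% at P = 5. All four are below 80%.

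**Step 6: regular injections only.** The same subject then has an average interval of P and 100% interval compliance for any n. The average weekly dose can keep the additional injections, because splitting an interval does not change the sum of days in its denominator.

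**The case against.** Several points on the other side hold, and they limit the claim.

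- **Frequency.** A reader might infer that adherent subjects on this regimen will generally be classed non-compliant. The documents do not support that. They give neither the frequency nor the timing of prevention doses, and a subject with few of them stays at or above 80%. Nor is it shown that both parts usually fail; at a 4-day interval under uniform timing they do so half the time.
- **The formula.** The dose-count numerator gives the milder rate n/(n+1), and the SAP does not say which definition governs.
- **The cross-reference.** The parenthesis in SAP 6.5.5.2 mentions only bleeds and surgical periods as separators, so one might argue that the rule on additional injections was not meant to carry over. But the reference is to 6.5.3 as a whole, and nothing exempts these injections.
- **The average interval.** A reader might call the 6.5.3 average wrong. It is a legitimate mean time between all prophylactic injections and a fair measure of injection burden. Replacing it outright would lengthen the reported interval.
- **SAP 5.3.2.** A reader might see a contradiction there. That rule handles long gaps resulting from missing data, which is a different purpose. Its remark that these doses are sporadic is relevant but does not conflict with 6.5.3.
- **Who is in the table.** Compliance is summarized for the overall prophylaxis regimen. SAP 6.5.1.2 describes that term, for another table, as tailored plus weekly. If this carried over, personalized subjects would not enter the compliance summary at all. Otherwise the effect is diluted by the other regimens.
- **Importance.** Neither measure is a listed endpoint in SAP 2.2, and no analysis set in SAP 4 depends on prophylactic compliance.

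None of this removes the defect: parts of a split interval are compared with a prescribed schedule that they were never meant to follow.

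**Conclusion.** The concern holds in a limited form. As SAP 6.5.3 and 6.5.5.2 are written, each permitted prevention dose creates at least one failing interval whenever the prescribed interval exceeds 2 days. A fully adherent subject falls below 80% if prevention doses occur at least once per 8 intervals (both parts failing) or once per 3 (one part failing, or the formula wording). Whether any subject reaches those frequencies cannot be judged from the documents.

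The splitting acts on interval compliance only. A dose-compliant subject who falls below the cut-off moves to the middle category, compliant on one measure, and not to the category for neither. The average interval is shortened by the factor n/(n+1) relative to the regular schedule. It is valid as defined, but it does not describe that schedule and is built differently from the other regimens.

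Bleeding rate, consumption and inhibitor results are unaffected. The change is worth making because the compliance rule gives a wrong answer for adherent subjects and is easy to correct.

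**What to change.** - **SAP 6.5.5.2:** evaluate interval compliance from consecutive regular prophylactic injections only, and reword the formula's numerator so that it counts intervals under the same definition as the text.
- **SAP 6.5.3:** keep additional injections in the average weekly dose. For personalized prophylaxis, report the average interval between regular injections alongside, not in place of, the all-injection average, with the number of additional injections per subject-year.
- **SAP 6.5.5:** state whether the overall prophylaxis regimen in the compliance tables includes personalized prophylaxis.

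The cost is a few sentences, a filter on the recorded reason for injection, and a small amount of extra programming. The result will depend on how reliably subjects label injections as regular or additional.
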